7.4. Secondary analyses

7.4.1. Aim 3: Evaluate associations between time of a women disclosing their HIV-infected status to their male partner and the trial endpoints: enrollment of the male partner, uptake of PrEP/ART; viral suppression

Descriptive analysis

- Tabulate the visit where the women first reported disclosure of her HIV-infected status to her partner
- For enrolled male partners, tabulate visit of first disclosure of male HIV status to his partner by male HIV status
- For women with enrolled partners, tabulate the joint disclosure of each partner by the end of the study

Statistical analysis

30 Sep 2021

- 1) Assess whether a woman's disclosure of HIV-infected status to her partner changes the probability of her male partner testing

Method: Time to event (event = male partner enrollment) Cox PH model with time varying covariate of women's disclosure. Disclosure is assessed as a cumulative time varying covariate, where a woman is considered disclosed if she self-reports disclosure at any time at or before the outcome is reported (i.e. if she reports disclosure at a visit before or at when her partner is enrolled). Women are assumed undisclosed until first visit she reports disclosure. Time is censored at the earliest of male partner testing (i.e. enrollment) or woman's last attended visit.

- 2) Assess whether male partner testing changes the probability of disclosure

Method: Time to event (event = woman's first report of disclosure) Cox PH model with time varying covariate of male partner enrolled. Women who self-report disclosure at baseline are excluded. Time is censored at the earliest of first disclosure or woman's last attended visit.

- 3) Assess whether a woman's disclosure of HIV-infected status to her partner changes the probability of initiation of PrEP/ART in her partner

Method: Same as 1) above, only with event = male partner initiated ART/PrEP. Analysis may be conducted in the entire v=cohort, and restricted to women with an enrolled partner

- 4) Assess whether a woman's disclosure of HIV-infected status to her partner changes VS of women

Method: Repeated measure analysis of outcome viral suppression in women. At each measurement of VL, primary time-varying covariate is whether the women has disclosed to her partner at or prior to the measurement. GEE model for probability of the outcomes will be used, including all visits where outcome is reported. Baseline viral loads are included

In all of the above models, adjustment for the following covariates will be considered (as appropriate):

- Age (in categories)
- Viral suppression at baseline
- Trimester of pregnancy at enrollment
- Randomization arm
- Women's prior knowledge of her HIV status
- Male Partner HIV status Negative, Positive, not known.

Additional variates may be considered if evidence of confounding is found (greater than 10% change in estimated effect).

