#### For men

- In partnership with an HIV-positive pregnant woman in PMTCT B+

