#### Benefits

The primary aim of this study is to evaluate the impact of innovative strategies on male partner HIV testing, engagement in HIV care and prevention among men, and on post-partum ART continuation and adherence among HIV-positive women. HIV prevention practices, according to Ugandan guidelines, will be provided to all participants enrolled in this study. This will include risk reduction counseling, treatment of sexually transmitted infections (STIs), condoms, and referral for medical male circumcision. If prevention strategies are modified during the course of study conduct (e.g. PrEP becomes available through the public health system), participants will be counseled and referred for these strategies as well.

HIV-positive women will benefit from male partner testing, facilitated disclosure and ART counseling. HIV-negative male partner participants will benefit by having free access to PrEP during the study period, until 6 months after their partner initiates ART. Participants may benefit from ongoing access to prevention services. There may be no other direct benefits to participants in this study. However, participants and others also may benefit in the future from information learned from this study.

All participants will be provided with HIV prevention services, including condoms, STI treatment, and ongoing support, including counseling and referral to other support services.

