2.1.2. Secondary Objectives

- Evaluate whether HIV testing combined with offer of PrEP for HIV-negative male partners and ART uptake for HIV-infected male partners increases effective post-partum ART use among HIV-infected Ugandan women in PMTCT B+.
- As a women's HIV disclosure to her partner is hypothesized to be the mechanism for increasing her effective ART use, we will evaluate associations between first visit a women reported disclosure of their HIV-infected status to their male partner and the trial endpoints: enrollment of the male partner, uptake of PrEP/ART; viral suppression. We will also assess whether male partner testing, HIV status and disclosure, impact trial endpoints.

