7.3. Analysis of the Primary Endpoints

7.3.1. Aim 1a Difference in male partner testing between arms

Endpoint: HIV testing at the study site of a woman's male partner. HIV testing at the site is synonymous with male partner enrollment.

Descriptive analyses:

- We will tabulate the proportion of women with male partner enrollment by the end of the study by arm, and the resulting HIV status (by study testing) of the male partners at enrolment.
- We will tabulate the proportion of men who have been HIV tested, and their HIV test result, according to the women's self-report, by arm. Note that as the HIVST arm provides a test for men at home, this comparison has potential for ascertainment bias.

Statistical analysis

We will use Kaplan-Meier curves to depict the time from women's enrollment until her male partner's site HIV test (i.e. enrollment) by study arm.

We will assess the difference between arms using a time to event analysis of time of randomization of the pregnant women until the event of her male partner's HIV test at enrollment. A Log-rank test will be used to assess the statistical significance of difference between arms; Cox proportional hazard regression will be used to estimate the HR and 95% CI. The Kaplan Meier curve will be used to assess the proportion of male partners tested at 6 and 12 months after female partner randomization. Pointwise confidence intervals will be computed assuming the normal approximation, using the standard error of the estimate from the KM curve.

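### SAP 7.4.1 counts disclosure first reported at the event visit as exposure before the event, so disclosure prompted by partner testing can appear as a cause of testing

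*SAP*

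**What the plan says.** SAP 7.4.1 analysis 1 fits a Cox model for time to male partner enrolment, with the woman's disclosure of her HIV status as a cumulative time-varying covariate. She counts as disclosed "if she reports disclosure at a visit before or at when her partner is enrolled". The covariate starts at the visit of report: "Women are assumed undisclosed until first visit she reports disclosure". No disclosure date, lag or sensitivity analysis on the ordering is described.

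Analysis 3 inherits the rule: "Method: Same as 1) above, only with event = male partner initiated ART/PrEP". Analysis 2 looks at the opposite direction: "Assess whether male partner testing changes the probability of disclosure".

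Under SAP 7.3.1, "HIV testing at the site is synonymous with male partner enrollment". Protocol Table 6 puts the test result, post-test counselling, PrEP provision and ART referral or provision at the man's enrolment visit. Protocol Table 1 puts couples counselling on serodiscordance at enrolment. The Protocol's Benefits section names testing and disclosure support together: "HIV-positive women will benefit from male partner testing, facilitated disclosure and ART counseling".

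**The concern.** A time-varying Cox covariate should carry only what was known before the event. Here the event visit itself can generate the exposure: the man tests, the couple is counselled, the woman discloses, and she is then coded as having been disclosed when he tested. Women without an event report disclosure at their own visits too, but they have no enrolment to prompt it. Any excess disclosure prompted by enrolment is therefore credited to the exposed side of the comparison.

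Analyses 1 and 3 are worded as whether disclosure changes the probability of testing or of initiation. With this coding they could answer yes when only the reverse is true. The adjustment covariates listed at the end of SAP 7.4.1 do not address the order of events. Elsewhere the SAP does impose an order: Aim 2b requires PrEP/ART initiation at least 3 months before the viral load.

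**Working it through.** **Plan figures.** The documents give no power or effect size for these models, so there is nothing to reproduce. As an input check, 2:1 allocation with 30% and 55% uptake gives (30 + 2 × 55)/3 = 46.7%, matching the 47% in Protocol Table 4.

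**Closed form under no true effect, visits aligned.** At an event visit, let *p* be the share of women without the event who have reported disclosure by then. Let *s* be the share of enrolments that prompt disclosure in a woman otherwise undisclosed. Cases are then exposed with probability p + (1 − p)s. The exposure odds in cases divided by those in non-cases approximate the hazard ratio:

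HR ≈ [1 + s(1 − p)/p] / (1 − s)

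At s = 0 this is 1, so the rule alone adds nothing.

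Assumed inputs (none is in the documents): 40% disclosed at baseline and 10% of undisclosed women disclosing per visit. At the third visit p = 1 − 0.6 × 0.9³ = 0.56, so (1 − p)/p = 0.44/0.56 = 0.786.

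- s = 0.10: (1 + 0.079)/0.90 = 1.20
- s = 0.30: (1 + 0.236)/0.70 = 1.77
- s = 0.60: (1 + 0.471)/0.40 = 3.68

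If 30% or 60% is instead the total share of undisclosed women who disclose at the enrolment visit, including the 10% background, then s = 1 − 0.70/0.90 = 0.222 or s = 1 − 0.40/0.90 = 0.556. The results are (1 + 0.175)/0.778 = 1.51 and (1 + 0.437)/0.444 = 3.23.

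**Simulation under no true effect, analysis 1 only.**

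- Same disclosure inputs, 10% partner enrolment per visit, six visits, total shares of 10%, 30% and 60%: HR 1.00, 1.50 and 3.08.
- A second run on assumed inputs, with 0%, 10%, 30% and 60% of enrolments prompting disclosure: HR 1.03, 1.21, 1.73 and 3.51; rejection at nominal 5% of 5%, 29%, 96% and 100%. Counting only earlier-visit disclosure gave HR about 1.0 and rejection of 5 to 8%.

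**Visits not aligned across women.** Taken from the documents: 500 women, 2:1, 30% against 55% uptake at one year, 12 to 18 months of follow-up, 3-monthly visits. Assumed: 20% or 50% disclosed at baseline, 5% or 10% new disclosure per quarter, enrolment on any day.

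| Enrolments prompting same-day disclosure | HR, rule as written | Rejection |
|---|---|---|
| 0% | 1.04–1.15 | 5–22% |
| 10% | 1.26–1.54 | 45–88% |
| 25% | 1.66–2.40 | 97–100% |
| 50% | 2.9–5.1 | 100% |

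The excess at 0% arises because cases are updated on the event day while the other women carry forward an older report. On a shared visit grid the 0% case returns to HR 0.99.

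**Earlier-visit rule, same settings.** HR is 0.98 to 1.01 and rejection 4 to 7% when enrolment can fall on any day. If enrolments fall only on the woman's own visit days, HR is 0.86 to 0.97 and rejection 5 to 20%, because the case's last usable report is then a full interval old.

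**Cost when disclosure truly matters.** With no prompting and a true HR of 2.0, the present rule recovers 2.00 and the earlier-visit rule gives about 1.8. With a true HR of 4.0 the figures are 4.02 and 3.17.

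**The case against.** The strongest reply is that a same-visit report often describes a disclosure that did come first. Post-partum visits are three months apart. A woman who discloses between visits and then brings her partner can first report it on the day he tests. The present rule classes her correctly and an earlier-visit rule does not. This stands, and it is why the stricter rule attenuates true effects and why neither rule should be shown alone.

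A reader might infer that the rule by itself guarantees an association. It does not: with aligned visits and no excess disclosure at enrolment, the hazard ratio is about 1. The bias needs prompted disclosure, or updating of cases only on the event day. The documents make both plausible, since visits follow gestation and delivery and testing comes with counselling, but they quantify neither.

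A reader might also infer that the trial's test of its proposed mechanism is undermined. The SAP does call disclosure "hypothesized to be the mechanism for increasing her effective ART use", but that concerns the woman's ART use, not partner testing, and so does not bear on analyses 1 and 3. SAP 2.1.2 and the 7.4.1 heading also speak of associations, and analysis 2 sits alongside, so the reverse direction is not hidden.

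Finally, in the self-test arm a man may test at home before his site test. Disclosure prompted by that test could be reported at an earlier visit and would survive the stricter rule. This limits the remedy but does not defend the present coding.

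**Conclusion.** The point holds as a conditional one. The SAP text places event-visit reports on the exposed side in analysis 1 and, by reference, in analysis 3. If enrolment prompts disclosure, the estimated effect of disclosure is biased upward. With aligned visits the null hazard ratio is about 1.0, 1.2, 1.5 to 1.7 and 3.1 to 3.5 at 0%, 10%, 30% and 60% prompted. The ranges at 30% and 60% reflect whether the share includes or adds to background disclosure. With unaligned visits the bias is larger. Every figure rests on assumed disclosure rates and was computed for analysis 1 only; analysis 3 shares the rule, but its size was not worked out.

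It would be tempting to conclude that partner enrolment should be lagged in analysis 2 as well. The documents state no same-visit rule there, and a lag would move test-prompted disclosures into unexposed time. In simulation with 30% or 60% prompted, a hazard ratio of 2.3 or 5.2 became 0.77 or 0.64, reversing the sign of a real effect.

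These are secondary, non-randomised analyses. The arm comparisons in Aims 1a to 1c and the Aim 2 analyses do not use this covariate rule and are unaffected.

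**What to change.** For analyses 1 and 3 in SAP 7.4.1:

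- In the main model, count disclosure only if it was reported at a visit before the event visit, or is dated before the event if a disclosure date is collected. Dates are preferable where enrolments fall on the woman's own visit days.
- Report, for each analysis, the number of events with first disclosure reported at the event visit.
- Keep the at-or-before rule as a labelled sensitivity analysis, and present the two results as a range.

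Leave partner enrolment unlagged in analysis 2.

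The cost is a few sentences of SAP text and one further model for each of the two analyses, with no new data collection unless dates are added. The statistical cost is more than a small loss of precision: disclosures that truly fell between visits and preceded testing are counted as unexposed, pulling a true hazard ratio of 2.0 to about 1.8.

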#### Antenatal and postnatal care

Data collection will occur during standard of care antenatal/postnatal visits. HIV-positive pregnant women will access routine care at antenatal clinics according to guidelines for preventing and treating HIV infection in Uganda [71]. Pregnant women will have up to 4 antenatal visits before delivery: 1 visit in the first trimester, 1 visit in the second trimester and 2 visits in the third trimester. The standard-of-care antenatal package includes cotrimoxazole preventive therapy, nutrition assessment, iron, folic acid and multivitamin supplementation and screening for syphilis. Women newly initiating ART in PMTCT B+ will have same-day pre-ART adherence counselling and ART initiation (Table 1). They will have PMTCT B+ follow-up visit two weeks after initiating ART, and monthly visits for ART refills thereafter until delivery. Women will be offered delivery at a facility of their choice. After delivery, women will be followed quarterly for up to 12 months.

Brief study questionnaires will be administered will occur at the PMTCT visits to avoid separate study-specific visits. Postnatal care and infant immunization visits will follow the routine maternal and child health (MCH) schedule. Viral load (VL) monitoring will include plasma HIV RNA levels at enrollment, 6 and 12 months post-partum. Blood samples will be batch-tested at collaborating laboratories. Women will be asked about interruptions in ART use. If the mother is stable on ART with good adherence and undetectable VL, post-partum visits will be quarterly thereafter. During clinic visits, women will complete interviewer-administered surveys to collect data on behavioral factors that could mediate women's post-partum use of ART. Women will be provided their viral load results at the next visit with counseling about the relationship between adherence, viral load and transmission risk.

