3.4. Assessments

3.4.1. Male visit schedule:

Every three months after enrollment up to 12 month post-partum. Men will undergo informed consent for HIV testing and referral for HIV care and ART if they test HIV-positive, or offered PrEP if they test HIV-negative.

3.4.2. Pregnant women schedule:

Antenatal visit schedule to align with the PMTCT schedule. One visit expected every trimester. Study visits occur every three months after birth (post partum). Viral load (VL) monitoring will include plasma HIV RNA levels at enrollment, 6 and 12 months post-partum.

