5.2.2. Use in analysis

Key predictors

- 1) Study arm: HIVST (Intervention arm) versus Letter (standard of care arm). Assigned at randomization of the women.

30 Sep 2021

- 2) Partner enrolled (time varying): whether male partner was enrolled prior to the current visit.
- 3) Uptake of PrEP/ART of partner (time varying):
 - a. A woman has a partner with PrEP/ART uptake at her visit if her partner knows his HIV status and is either on ART (if HIV-positive) or initiated PrEP (if HIV-negative) prior to that visit. Both male partners who do not enroll and male partners who do not initiate ART or PrEP are defined as no uptake of PrEP/ART. In analyses that use time to PrEP/ART, time of first report of PrEP/ART will be used.
 - b. An alternative definition will also define any HIV-negative men with partners who are virally suppressed as on PrEP/ART. A female partner is defined as being VS if she is virally suppressed at assessments both before and after the visit.
- 4) Disclosure of HIV-infected status to male partner self-reported at baseline

Effect modifiers:

- 1) Viral suppression of woman (time varying, measured at baseline, 6 and 12 mo)
- 2) Trimester of pregnancy at enrollment
- 3) Partner ever tested for HIV (time varying: reported by female partner)
- 4) Mutual disclosure status of HIV (time varying, as reported by each partner). If no enrolled male partner, mutual disclosure is assumed to not occur.
- 5) Male HIV status. If a male partner does not receive HIV testing from the study site, it is assumed their HIV status is unknown to both members of the coupleStudy Population

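### Aim 3 analysis 2 cannot tell a disclosure that led to the partner's test from one that followed it within the same visit gap, so it leans towards testing prompting disclosure

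*SAP*

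**What the plan says.** SAP 2.1.2 sets the aim: "we will evaluate associations between first visit a women reported disclosure of their HIV-infected status" to the male partner and the trial endpoints. SAP 7.4.1 then pairs two models. Analysis 1 asks whether disclosure changes partner testing; analysis 2 asks whether partner testing changes disclosure.

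For analysis 2 the specification is "Method: Time to event (event = woman's first report of disclosure) Cox PH model with time varying covariate of male partner enrolled". Women who report disclosure at baseline are excluded. Under analysis 1 the SAP adds: "Women are assumed undisclosed until first visit she reports disclosure".

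The exposure is defined in SAP 5.2.2: "Partner enrolled (time varying): whether male partner was enrolled prior to the current visit".

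On visit spacing, SAP 3.4.2 says of the antenatal period "One visit expected every trimester", with quarterly visits once she has delivered. The protocol (Antenatal and postnatal care) describes, for women newly starting ART, "monthly visits for ART refills thereafter until delivery", with study questionnaires given at PMTCT visits.

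For analysis 2 the SAP gives no date of the disclosure itself, no lag, no interval-censored model and no rule for ties. The adjustment list that closes 7.4.1 contains nothing about the order of events.

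**The concern.** Take a woman who discloses in week 2 of a three-month gap. Her partner comes to the site in week 6, and she reports the disclosure at her visit in week 12. The true order is disclosure, then test. The data for analysis 2 show a partner already enrolled and then a disclosure event.

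Such cases push the hazard ratio up when disclosure makes his attendance more likely. The SAP takes that path seriously, since analysis 1 is there to test it. The stronger the effect analysis 1 is looking for, the more of it leaks into analysis 2 with the direction reversed. At stake is the directional reading of a positive result: the report could say that testing men prompts their partners to disclose when only the opposite had happened.

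Excluding women who disclosed by baseline does not help, because the misordering arises after baseline.

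**Working it through.** The documents state no sample size, rate or effect for this analysis, so there is no figure to reproduce. The check asks what the planned model returns when testing truly has no effect on disclosure (true HR 1).

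**Inputs from the documents.** Event at the first report; exposure as enrolled before the current visit; visits about 0.25 year apart; two-sided 5% test (SAP 7.1); follow-up of 1 to 1.5 years (SAP 3.2.1).

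**Assumed, not in the documents.** 350 women undisclosed at baseline. Disclosure hazard 0.8 per year, so 1 − exp(−0.8) = 55% disclose by one year. Partner enrolment hazard before disclosure 0.3 per year, so 1 − exp(−0.3) = 26% by one year, inside the SAP's 20-30% standard-of-care range. Disclosure multiplies the enrolment hazard by θ.

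**Hand approximation.** Let g be the gap and h the enrolment hazard before disclosure.

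1. A woman who does not disclose in the gap has a chance of about h·g that her partner enrols in it.
2. A woman who discloses at a random point in the gap spends on average half of it at h and half at θh. Her chance is about h·g·(1 + θ)/2.
3. Partners enrolled in the current gap are therefore over-represented among women who report, by (1 + θ)/2. Partners enrolled in earlier gaps are not.
4. If f is the share of exposed woman-visits where he enrolled in the current gap, HR ≈ (1 − f) + f(1 + θ)/2 = 1 + f(θ − 1)/2.
5. With g = 0.25 there are six visits in 1.5 years. At visit k the exposed weight is exp(−0.2(k − 1))·[1 − exp(−0.075k)]; the newly enrolled weight is exp(−0.275(k − 1))·[1 − exp(−0.075)].
   - Exposed: 0.072 + 0.114 + 0.135 + 0.142 + 0.141 + 0.133 = 0.737.
   - New: 0.072 + 0.055 + 0.042 + 0.032 + 0.024 + 0.018 = 0.243.
   - f = 0.243/0.737 = 0.33.

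**Simulation with the same rates, three-monthly visits.** Ranges cover runs that differ in follow-up and tie handling.

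| θ | HR by hand, 1 + 0.33(θ − 1)/2 | HR simulated | False positives |
|---|---|---|---|
| 1 | 1.00 | 0.98-1.02 | no bias |
| 1.5 | 1.08 | 1.08-1.10 | 7-9% |
| 2 | 1.17 | 1.16-1.21 | 15-18% |
| 3 | 1.33 | 1.34-1.43 | 48-57% |
| 5 | 1.66 | 1.68 | 95-96% |

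**Other rates.** With about 40% of partners tested by 12 months, 30-70% of women disclosing by then, and 15 months of follow-up, the HR is about 1.23 (θ = 2), 1.61-1.69 (θ = 4) and 2.28-2.58 (θ = 8). At 50% disclosing, the share of reports made after his enrolment in which disclosure really came first is 18%, 30%, 46% and 62% for θ = 1, 2, 4 and 8. The θ = 1 case shows that misordering alone is harmless: 18% of those reports are out of order, yet the HR is about 1.00.

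**What reduces it.** At θ = 3, monthly visits give HR 1.14-1.15 with 11-21% false positives. If half of enrolments fall on her visit day (assumed, and not exposed because the definition says prior to the visit), HR is 1.22 with 24%; at 80% it is 1.14 with 11%. With 150 undisclosed women and three-monthly visits, false positives at θ = 3 fall to 28%.

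**Lagging exposure to her previous visit.** Across these settings HR is 0.99-1.01, with 2-7% false positives.

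**Cost of the lag.** Suppose testing does prompt disclosure: half of undisclosed women disclose within weeks of his test, with no reverse effect. One run gives an unlagged HR of 2.5 (power 100%) and a lagged HR of 1.16 (power 9%). A second run of a prompt effect gives 2.1 (99%) against 1.11 (7%). If half of enrolments fall on her visit day, the lagged HR in the first setting recovers to 1.98 (82%).

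**The case against.** Four points on the other side have force.

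- **The size rests on assumptions.** Neither document gives the number of women undisclosed at baseline, the disclosure rate or θ. At θ of 1.5 to 2 the planned model would usually not reach significance. This stands, and the size should be read as a conditional range.
- **Visits may be closer, or attended together.** Monthly refill visits apply to women newly starting ART, until delivery. Control-arm letters invite partners to test alone or as a couple, and women with untested partners are encouraged to come with them. Both reduce the bias. Post-partum visits remain quarterly.
- **A lag has its own error.** Disclosure soon after his test, perhaps in couple counselling, is the likeliest way for testing to have an effect, and the lagged model credits it to the unexposed state. This stands and rules out the lag as a replacement.
- **It is one of four secondary, non-randomised models** under a heading about associations. That is true and limits the weight of the point. But the stated question for analysis 2 is whether testing changes the probability of disclosure, which is directional.

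A reader might also infer that the SAP dates the covariate at his exact enrolment date. It does not say so for analysis 2. Aim 1a runs its clock from "time of randomization of the pregnant women until the event of her male partner's HIV test at enrollment", but that is another analysis. Nothing turns on it: events occur only at her visits, so an exact date and the SAP 5.2.2 definition assign the same exposure at each event.

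**Conclusion.** The point holds as a conditional one. As written, analysis 2 is biased upward if disclosure raises partner testing, because disclose-enrol-report sequences inside one gap are scored as testing before disclosure. Under the assumed rates and three-monthly visits, a true HR of 1 appears as about 1.1, 1.2, 1.35 and 1.7 for θ of 1.5, 2, 3 and 5, with false positives of roughly 7%, 17%, 50% and 95%. The direction of the bias is firm; its size depends on quantities the documents do not give.

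A reader might go further and conclude that analysis 2 will report testing as prompting disclosure whatever the truth. The documents do not support that: without a disclosure-to-testing effect there is no bias, and with a modest one the test usually stays non-significant. Nor do they support concern for the main results. The Aim 1 arm comparisons do not use the date of disclosure and are unaffected.

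**What to change.** Add to SAP 7.4.1, analysis 2, that the model is fitted twice: as planned, and with enrolment status lagged to her previous visit, so that a disclosure first reported at visit v counts as exposed only if he enrolled by visit v−1. Present the two estimates as a pair. Conclude that testing prompts disclosure only if the lagged estimate also supports it; otherwise describe an association of uncertain order. State also how an enrolment on the day of her visit is counted.

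This costs a sentence or two and needs no new data. A lagged exposure is already used in the SAP: Aim 2b (7.3.5) requires the partner's PrEP or ART initiation to precede the viral load by at least three months. The downside is that the lagged model can miss a prompt effect almost entirely, so a null lagged result beside a positive unlagged one leaves the order unresolved and does not show that testing has no effect. For that reason the lagged model should accompany the planned one and not replace it.

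### The Aim 3 model of disclosure and viral suppression pools enrollment and post-partum viral loads without a visit term, so any time trend in suppression appears as a disclosure effect

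*SAP*

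**What the plan says.** SAP 7.4.1, item 4, asks whether a woman's disclosure of her HIV status to her partner changes her viral suppression. It is a repeated-measures analysis: "GEE model for probability of the outcomes will be used, including all visits where outcome is reported. Baseline viral loads are included". The closing words, "Baseline viral loads are included", make enrollment an outcome row. The exposure is defined as follows: "At each measurement of VL, primary time-varying covariate is whether the women has disclosed to her partner at or prior to the measurement". Under SAP 3.4.2 the measurement times are enrollment, 6 and 12 months: "Viral load (VL) monitoring will include plasma HIV RNA levels at enrollment, 6 and 12 months post-partum".

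The covariate list at the end of 7.4.1 serves all four Aim 3 models: "In all of the above models, adjustment for the following covariates will be considered (as appropriate"). It holds age, "Viral suppression at baseline", trimester at enrollment, randomization arm, prior knowledge of HIV status and partner HIV status. It has no visit, post-partum month, time since enrollment or ART duration. Trimester at enrollment is fixed for each woman and cannot absorb change between her visits. One further route is left open: "Additional variates may be considered if evidence of confounding is found (greater than 10% change in estimated effect").

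The neighbouring Aim 2b analysis (SAP 7.3.5) uses only the 6- and 12-month viral loads as outcomes.

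**The concern.** Enrollment rows contain the fewest disclosed women, because disclosure is coded cumulatively. If suppression at enrollment differs from suppression later, pooling the rows without a visit term compares early rows with late rows and attributes the difference to disclosure.

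There are reasons to expect a trend. Women who test positive are given ART immediately (Protocol, Recruitment), and the Protocol's account of PMTCT B+ in Uganda reports 90% undetectable after more than 6 months of ART. Both point to a rise. The Protocol's concern about post-partum discontinuation points the other way.

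A second problem arises if baseline suppression is used as a covariate here. On the enrollment row it is then the outcome itself. If the covariate uses the 50-copy cut-off in SAP 7.2 and the outcome uses the 400-copy cut-off in SAP 2.2.1, covariate = 1 still forces outcome = 1.

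SAP 2.1.2 names disclosure as the hypothesized mechanism for effective ART use, and item 4 is the model that links disclosure to suppression. It would be tested at two-sided 0.05 without multiplicity adjustment (SAP 7.1). An artefact of time could be reported as support for the mechanism, or as evidence against it.

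**Working it through.** The documents state no effect size or power for this model, so there is no planned figure to reproduce.

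**Inputs from the documents.** 500 women; viral load at enrollment, 6 and 12 months; cumulative disclosure; two-sided alpha 0.05.

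**Assumptions.** Suppression p and cumulative disclosure d at each visit are not given and are varied below. Disclosure is independent of viral load, so the true odds ratio is 1.

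**Closed form.** With equal numbers at each visit and independence working correlation, the pooled model without covariates estimates

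OR = [Σ d·p / Σ d·(1−p)] ÷ [Σ (1−d)·p / Σ (1−d)·(1−p)], summed over the three visits.

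*Rising, p = 60/85/85%, d = 40/60/70%.*
- Disclosed rows sum to 1.70 per woman. Suppressed: 0.240 + 0.510 + 0.595 = 1.345; not suppressed: 0.355; odds 3.789.
- Undisclosed rows sum to 1.30. Suppressed: 0.360 + 0.340 + 0.255 = 0.955; not suppressed: 0.345; odds 2.768.
- OR = 3.789 / 2.768 = 1.37.

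*Falling, p = 90/85/75%, same d.*
- Disclosed: 0.360 + 0.510 + 0.525 = 1.395 against 0.305; odds 4.574.
- Undisclosed: 0.540 + 0.340 + 0.225 = 1.105 against 0.195; odds 5.667.
- OR = 4.574 / 5.667 = 0.81.

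*Flat, p = 85% throughout.* Both odds are 0.85/0.15, so OR = 1.00.

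**Simulation under the null.** Logistic GEE, independence working correlation, robust standard errors, 500 women, within-woman latent correlation 0.5 (assumed). Entries are the odds ratio with the false rejection rate in brackets.

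| Suppression, % | Disclosure, % | Pooled, no visit term | Pooled + baseline suppression | All rows + visit term |
|---|---|---|---|---|
| 60/85/85 | 40/60/70 | 1.37 (about 65%) | 1.57 | 1.00 (5%) |
| 90/85/75 | 40/60/70 | 0.80 (about 27%) | – | about 1.0 (about 5%) |
| 85/85/85 | 40/60/70 | about 1.0 (about 5%) | – | about 1.0 (about 5%) |
| 50/85/85 | 30/60/75 | 1.84 (100%) | 2.32 (100%) | 1.00 (3.5%) |
| 75/88/88 | 30/60/75 | 1.38 (59.5%) | 1.59 (82%) | 1.00 (7.0%) |
| 75/88/88 | 60/70/75 | 1.12 (12%) | 1.18 (17.5%) | 0.99 (4.0%) |
| 90/85/75 | 30/60/75 | 0.73 (56%) | 0.67 (68%) | 1.00 (4.5%) |

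In every trend scenario where it was run, adding baseline suppression without a visit term moved the odds ratio further from 1.

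The SAP does not name a working correlation. An exchangeable structure does not help: in the first scenario it gives about 1.60 with about 95% false rejection.

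**Precision of the two valid models, first scenario.** The standard error of the disclosure log odds ratio is 0.153 with all rows plus visit, and 0.212 with post-partum rows plus baseline suppression plus visit. The variance ratio is (0.212/0.153)² = 1.92. The two models condition on different things, so this comparison is approximate.

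**The case against.** Four arguments favour the plan.

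*The direction of the bias is not known.* This stands. A reader might infer that the model must produce a false positive. The documents do not support that. SAP 7.2 anticipates women on ARVs before pregnancy and women already suppressed at baseline, which would flatten the trend. The Protocol cites discontinuation by one-third to one-half of women after delivery, reports 60% retention at 12 months in the Mulago program, and assumes 50% continuation and suppression in its Aim 2 power calculation. A fall is plausible too.

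*The baseline covariate is optional.* This also stands. The list is generic, is to be considered as appropriate, and three of its four models are Cox models in which baseline suppression causes no such problem. A reader might infer that the plan commits to regressing the enrollment outcome on itself; it only permits this. Leaving the covariate out removes the self-regression but not the time confounding.

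*The 10% rule could bring in a visit term.* In the first scenario the change is (1.37 − 1.00)/1.37 = 27%, so the trigger would be met if visit were tried. But the rule says only that additional variates may be considered, and it does not name visit. It is a possible rescue, not a pre-specified safeguard.

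*The analysis is secondary and described as an association.* True, and this limits the stakes. A null test that rejects about 65% of the time is still not a usable test of association.

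Two stronger remedies might also be inferred: that enrollment rows are uninformative and must go, and that disclosure must be redefined as strictly before each measurement. The precision figures contradict the first. Nothing in this defect or in the simulations calls for the second.

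**Conclusion.** The concern holds in a conditional form. As written, item 4 pools enrollment and later viral loads against an exposure that can only increase, with no term for time. Its disclosure coefficient is biased whenever suppression changes over the visits. The bias follows the trend: upward with a rise, downward with a fall, absent if suppression is flat.

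Under the assumed rates the false odds ratio ranges from 0.73 to 1.84 without the baseline covariate, and from 0.67 to 2.32 with it. The mildest trend tested gives only 1.12. All of these depend on assumed suppression and disclosure rates and an assumed within-woman correlation. The gap in the text is certain; the sign and size in this trial are not. The randomized comparisons in Aim 1 and the analyses of Aim 2 are unaffected.

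**What to change.** In SAP 7.4.1, item 4:

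1. Add visit (enrollment, 6 months, 12 months) as a categorical term that is always in the model, not subject to the 10% rule.
2. State that baseline suppression is not a covariate while baseline is an outcome row.
3. State one suppression threshold for this model, since the SAP uses both 50 and 400 copies elsewhere.

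The visit term is what removes the bias; the second change removes the self-regression. A valid alternative to keeping the enrollment rows is to restrict outcomes to 6 and 12 months, as Aim 2b does, keep baseline suppression as a covariate and include visit. That costs precision: a standard error of about 0.21 against 0.15 in the first scenario.

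The recommended change is a few words in the SAP, with no new data.
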